9.8.2 Rash

Individuals who develop a generalized rash will be monitored closely. Study drug dosing should be interrupted if a subject develops a generalized rash of Grade 3 or higher, or a rash that is considered a serious adverse event (SAE). The investigator will notify the medical monitor of any rash that results in interruption of study drug, is Grade 3 or higher (Section 13.1.1.4), or is an SAE. Investigators should consider additional evaluation including laboratory testing (e.g., complete blood count with differential, liver function test), photographs of the rash, and dermatology consultation. The investigator may consider resumption of study drug if clinically appropriate.

9.9 Removal of Subjects

Subjects may withdraw from the study at any time at their own request. Subjects may be withdrawn from study drug treatment at any time at the discretion of the investigator or Vertex for safety, behavior, noncompliance with study procedures, or administrative reasons. A subject who prematurely terminates study drug treatment will continue to be followed, unless the subject withdraws consent (or assent, when applicable).

In addition, a subject must be discontinued from study drug treatment if the subject meets either of the following criteria, and should return for study assessments as noted in Section 9.1.5.2:

- Meets any of the stopping (discontinuation) criteria (Section 9.8)
- Becomes pregnant (Section 11.6.7.2)

Other criteria that require subjects to be discontinued from study drug treatment are:

- If a subject is identified after randomization as having been enrolled to the incorrect comparator group, the subject must be discontinued from the study.

If a subject does not return for a scheduled visit, reasonable effort will be made to contact the subject. In any circumstance, reasonable effort will be made to document subject outcome. The investigator will inquire about the reason for withdrawal, request that the subject return all unused investigational product(s), request that the subject return for an ETT Visit and Safety Follow-up Visit, if applicable (see Section 9.1.5), and follow up with the subject regarding any unresolved AEs.

If a subject withdraws consent or assent for the study, no further assessments will be performed. Vertex may retain and continue using the study data and samples after the study ends, and may use the samples and information in the development of the study compounds, for other drugs and diagnostics, in publications and presentations, and for education purposes. If a subject withdraws from the study, the study data and samples collected will remain part of the study. A subject will not be able to request the withdrawal of his or her information from the study data. A subject may request destruction of the samples collected from him or her during the study as long as those samples can be identified as his or her samples.

9.10 Replacement of Subjects

Subjects who withdraw or are withdrawn before the first dose of study drug on Day 1 of the Treatment Period may be replaced.

Subjects who withdraw or are withdrawn for nonsafety reasons during the study drug treatment period(s) may be replaced at Vertex's discretion.

10 STUDY DRUG INFORMATION AND MANAGEMENT

During the Run-in Period, study drug refers to IVA and TEZ/IVA.

During the Treatment Period, study drug refers to VX-445/TEZ/IVA and matching placebo, TEZ/IVA and matching placebo, and IVA and matching placebo.

10.1 Preparation and Dispensing

Study drug may be dispensed only under the supervision of the investigator or an authorized designee and only for administration to the study subjects.

10.2 Packaging and Labeling

Study drug tablets will be supplied in blister cards by Vertex. Study drug labeling will be in compliance with applicable local and national regulations. Additional details regarding packaging, labeling, and dispensing for study drug will be in the Pharmacy Manual.

10.3 Study Drug Supply, Storage, and Handling

VX-445/TEZ/IVA will be supplied as 2 FDC film-coated tablets (100 mg VX-445/50 mg TEZ/75 mg IVA). Matching VX-445/TEZ/IVA placebo tablets will be of similar size and appearance and contain 0 mg VX-445, 0 mg TEZ, and 0 mg IVA (Table 10-1).

TEZ/IVA will be supplied as an FDC film-coated tablet (100 mg TEZ/150 mg IVA). A matching TEZ/IVA placebo tablet will be of similar size and appearance and contain 0 mg TEZ and 0 mg IVA (Table 10-1).

IVA (150 mg) will be supplied as a film-coated tablet containing 150 mg IVA. Matching IVA placebo tablets will be of similar size and appearance and contain 0 mg IVA (Table 10-1).

Blister cards must be stored under conditions noted in the Pharmacy Manual. The investigator, or an authorized designee (e.g., a licensed pharmacist), will ensure that all investigational product is stored in a secured area, under recommended storage conditions, and in accordance with applicable regulatory requirements. To ensure adequate records, all study drugs will be accounted for via the drug accountability forms, as instructed by Vertex.

Table 10-1 Study Drug: Dosing Form/Route/Strength

Drug Name, Dosing Form, Route	Tablet Strength
VX-445/TEZ/IVA, FDC tablet, oral	
VX-445	100 mg
TEZ	50 mg
IVA	75 mg
VX-445/TEZ/IVA-matching placebo, tablet, oral	0 mg
TEZ/IVA, FDC tablet, oral	
TEZ	100 mg
IVA	150 mg
TEZ/IVA-matching placebo, tablet, oral	0 mg
IVA, tablet, oral	150 mg

Table 10-1 Study Drug: Dosing Form/Route/Strength

Drug Name, Dosing Form, Route	Tablet Strength
IVA-matching placebo, tablet, oral	0 mg

FDC: fixed-dose combination; IVA: ivacaftor; TEZ: tezacaftor

10.4 Drug Accountability

The pharmacist or designated study site staff will maintain information regarding the dates and amounts of (1) study drug received; (2) study drug dispensed to the subjects; and (3) study drug returned by the subjects. Subjects will be instructed to return all used and unused materials associated with the study drug to the site. These materials will be retained at the site according to instructions provided by Vertex or its designee. The study monitor will review study drug records and inventory throughout the study.

If a site uses a site-specific drug accountability system and/or process, including processes associated with the destruction of returned materials, the process must be documented and approved by Vertex. The study monitor must review the drug accountability documentation on a regular basis. The study monitor will promptly communicate to Vertex any discrepancies he or she is unable to resolve with the site.

10.5 Disposal, Return, or Retention of Unused Drug

The study site staff or pharmacy personnel will retain all materials returned by the subjects until the study monitor has performed drug accountability. The investigator will ensure that the materials are destroyed in compliance with applicable environmental regulations, institutional policy, and any special instructions provided by Vertex. Destruction will be adequately documented.

10.6 Compliance

To ensure treatment compliance, the investigator or designee will supervise all study drug dosing that occurs at the site. At each visit, site personnel will review that the subject is compliant with study drug dosing and remind the subject of study drug dosing requirements. Compliance will also be assessed by ongoing study drug count.

If a subject demonstrates continued noncompliance of study drug dosing despite educational efforts, the investigator should consider discontinuing the subject from the study.

10.7 Blinding and Unblinding

This will be a double-blind study.

10.7.1 Blinding

All subjects (and their parents/caregivers/companions), site personnel (including the investigator, the site monitor, and the study team), and members of the Vertex study team will be blinded to the treatment codes.

Individuals who may be unblinded include only the following:

- Any site personnel for whom this information is important to ensure the safety of the subject in the event of a life-threatening medical emergency

- Any site personnel for whom this information is important to ensure the safety of the subject and her fetus in the event of a pregnancy
- Vertex Global Patient Safety (GPS) and Regulatory Affairs personnel to satisfy SAE processing and reporting regulations
- Vendor preparing the final (production) randomization list
- Vertex IWRS Manager
- Vertex Clinical Supply Chain
- IDMC
- Vendor preparing the unblinded analysis of data for safety review by the IDMC
- Bioanalytical contract research organization (CRO) analyzing PK samples and the Vertex bioanalytical personnel who is not a member of the study team but reviews raw data from the bioanalytical CRO. The Vertex bioanalytical study team member will continue to be blinded.

Access to Spirometry and SwCl Results:

During the conduct of the study, the Vertex study team will not have access to the spirometry or SwCl results after the first dose of study drug in the Treatment Period.

Shortly before any planned efficacy analysis is conducted, the spirometry and SwCl data will be reviewed for data cleaning purposes by a biostatistician who does not have access to the treatment codes.

Individual SwCl test results will not be disclosed to the study sites with the exception of the screening and Day -14 Visit values. Subjects and their parents/caregivers/companions should not be informed of study-related spirometry results until Vertex has determined that the study has completed (i.e., clinical study report [CSR] finalization), regardless of whether the subject has prematurely discontinued treatment.

10.7.2 Unblinding

At the initiation of the study, study site personnel will be instructed on the method for breaking the blind. The unblinding method will be either manual or electronic.

Unblinding of Individual Subject Treatment Assignments by Investigator for Medical Emergencies or Urgent Clinical Situations

Unblinding of the individual subject's treatment by the investigator will be limited to medical emergencies or urgent clinical situations in which knowledge of the subject's study treatment is necessary for clinical management. In such cases, investigators will use their best judgment as to whether to unblind without first attempting to contact the medical monitor to discuss unblinding. If investigators deem it unnecessary to unblind immediately, they will first attempt to contact the medical monitor to discuss unblinding. If investigators have tried but are unable to reach the medical monitor, they will use their best judgment, based on the nature and urgency of the clinical situation, and may proceed with unblinding.

Contact information for the medical monitor (or appropriate backup) will be in a separate document.

If a subject's treatment assignment has been unblinded for a medical emergency or urgent clinical situation, the medical monitor will be notified within 24 hours of the unblinding event. The reason and the date of the unblinding will be documented clearly in the subject's study file. Information about the treatment assignment obtained from the unblinding will be maintained in a secure location with controlled access and will not be shared with Vertex, the CRO, or any site personnel (other than the physician treating the subject). In addition, the investigator will consider whether the clinical event that prompted unblinding will be considered an SAE, according to the regulatory definitions or criteria for SAEs, and if so, submit an SAE report to Vertex GPS or designee, per Section 13.1.2.

Unblinding of Individual Subject Treatment Assignments by Vertex GPS or Designee for SAEs or Safety Concerns

Vertex GPS or designee will also unblind any SAE reports in compliance with regulatory reporting requirements. In addition, Vertex may, for matters relating to safety, unblind individual subjects at any time.

11 ASSESSMENTS

The schedule of assessments is shown in [Table 3-1](#) and [Table 3-2](#).

11.1 Subject and Disease Characteristics

Subject and disease characteristics include the following: demographics, medical history, height, and weight.

Medical history will be elicited from each subject and extracted from medical records during screening. Based on the medical history, the subject will be assessed for any disqualifying medical conditions as specified in the inclusion and exclusion criteria. The medical history will include a complete review of systems, medical and surgical histories, and any allergies.

Height and weight will be measured with shoes off. Following screening, height will be collected only for subjects ≤ 21 years of age on the date of informed consent.

11.2 Pharmacokinetics

11.2.1 Blood Sampling

Blood samples will be collected to determine plasma concentrations of VX-445, TEZ, M1-TEZ, and IVA. These samples may also be used to evaluate metabolites of VX-445 and IVA or additional metabolites of TEZ for further evaluation of the bioanalytical method, or for exploratory analyses that provide information on the metabolic pathways used by or affected by VX-445.

The Day 1, Day 15, and Week 4 predose PK samples should be collected within 60 minutes before dosing. The Week 8 predose PK sample should be collected within 60 minutes before dosing for subjects who are receiving their first dose of study drug in an open-label study on the same day as the Week 8 Visit. For subjects who are not entering an open-label study within 24 hours of the Week 8 Visit, the Week 8 sample should be collected approximately 12 hours after the evening dose of IVA before the Week 8 Visit.

All efforts should be made to obtain the PK samples during this specified window. Samples collected outside of the window will be considered protocol deviations.

For each visit with a PK blood draw, a record of study drug administration will be collected as described in Section 9.6. The collection date and exact time that each PK blood sample is drawn will also be recorded.

Samples from the PK sampling will be kept frozen by Vertex or its designee until all analyses have been completed and then disposed of according to Vertex or designee standard operating procedures.

11.2.2 Processing and Handling of Pharmacokinetic Samples

Detailed procedures for the collection of blood samples and further procedures for processing and handling of samples for PK analysis will be provided in the PK Sample Handling Guidelines.

11.2.3 Bioanalysis

Samples will be analyzed using validated analytical methods in compliance with Vertex or designee standard operating procedures. A description of the assays and validation data will be provided in separate reports.

11.3 Pharmacodynamics: Sweat Chloride

SwCl samples will be collected with an approved collection device. Each collection will occur before study drug dosing (Section 9.6.1). At each time point, 2 samples will be collected, 1 from each arm (left and right). Sweat samples will be sent to a central laboratory for testing and interpretation of results. Specific instructions for the collection, handling, processing, and shipping of SwCl samples to the central laboratory will be provided separately.

See Section 10.7.1 for information about access to SwCl results.

11.4 Exploratory Assessments

These data will be used for exploratory purposes. Detailed procedures for the collection, processing, storage, and shipment of samples for exploratory assessments will be provided in a separate document.

11.4.1 Pharmacogenomics

An optional single blood sample (DNA sample) will be collected for potential exploratory evaluation of correlations between DNA markers with PK, PD, treatment response, AEs, and biomarkers related to health and disease, including CF, for subjects who choose to participate in this assessment.

11.4.2 Inflammatory Mediators

Blood samples (inflammatory mediator samples) will be collected at the time points noted in Table 3-2 and tested to assess markers related to inflammation. These markers may include, but are not limited to, C-reactive protein, immunoglobulin G, white blood cell (leukocyte) count, and interleukin-8.

11.4.3 Other Blood Biomarkers

Serum from an inflammatory mediator sample and an additional blood sample for plasma will be collected and banked for potential future exploratory evaluation of other blood biomarkers (e.g., proteins, peptides, lipids, metabolites, etc.) in relation to PK, PD, treatment response, AEs, and various disease manifestations of CF.

A blood sample for RNA isolation will be collected as indicated in [Table 3-2](#) for potential exploratory evaluation of gene signatures associated with various disease manifestations of CF and/or treatment response.

11.4.4 Microbiology and Other Sputum Biomarkers

Sputum samples will be collected at the time points noted in [Table 3-2](#) from subjects who can produce a sample spontaneously, and each sample will be processed and frozen. This will establish a baseline for subjects who continue into an open-label study and allow for evaluation of microbiology analysis and sputum biomarkers (which may include, but are not limited to, qualitative and quantitative bacterial and viral assessments including genomic analyses, analysis of immune cells, inflammatory markers, proteins, peptides, lipids, and endogenous metabolites) in relation to PK, PD, treatment response, AEs, and various disease manifestations of CF.

11.5 Efficacy

11.5.1 Spirometry

Spirometry will be performed according to the American Thoracic Society Guidelines/European Respiratory Society Guidelines¹² and according to the additional guidelines that follow.

Pre-bronchodilator spirometry is defined as spirometry testing performed for subjects who have

- withheld their short-acting bronchodilators (e.g., albuterol) or anticholinergic (e.g., ipratropium bromide [Atrovent[®]]) for more than 4 hours before the spirometry assessment;
- withheld their long-acting bronchodilator (e.g., salmeterol) for more than 12 hours before the spirometry assessment; and
- withheld their once-daily, long-acting bronchodilator (e.g., tiotropium bromide [Spiriva[®]]) for more than 24 hours before the spirometry assessment.

During the Screening Period, spirometry assessments may be performed pre- or post-bronchodilator. At all other visits, all spirometry assessments should be performed pre-bronchodilator. During the Treatment Period, spirometry assessments must be performed before study drug dosing (Section [9.6.1](#)) at approximately the same time at each visit. In the event that a subject forgets to withhold bronchodilator(s), spirometry should be performed according to the following:

- If a subject's Day 1 spirometry assessment is pre-bronchodilator, but, on a subsequent visit, the subject forgets to withhold bronchodilator use, a post-bronchodilator spirometry assessment will be obtained for that visit only, and the visit will not be rescheduled.
- If, on Day 1, the subject forgets to withhold his or her dose of bronchodilator, spirometry should be performed post-bronchodilator, and all subsequent spirometric measurements (according to the schedule of assessments in [Table 3-2](#)) should be performed post-bronchodilator.
- Each spirometry assessment will be recorded in the source documents as pre- or post-bronchodilator.

All sites will be provided with spirometers to be used for all study assessments. Spirometry data will be transmitted to a centralized spirometry service for quality review. The investigator's

assessment of the spirometry results will be used for the screening assessment and determination of eligibility.

See Section 10.7.1 for information about access to spirometry results.

The measured spirometric values listed below will be converted to percent predicted values using the standard equations of GLI.¹¹

- Forced expiratory volume in 1 second (FEV₁) (L)
- Forced vital capacity (FVC) (L)
- FEV₁/FVC (ratio)
- Forced expiratory flow, midexpiratory phase (FEF_{25%-75%}) (L/s)

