9.1.5.2 Discontinuation During the Treatment Period

Subjects who prematurely discontinue study drug treatment during the Treatment Period will continue to complete all scheduled study visits for assessments following completion of the ETT Visit, as detailed in Table 3-2. These subjects will complete an ETT Visit and Safety Follow-up Visit (as applicable; see Section 9.1.5).

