9.2.7 Important Protocol Deviations

An important protocol deviation (IPD) is a deviation that may significantly affect the completeness, accuracy, or reliability of the study data or that may significantly affect a subject's rights, safety, or well-being. IPD rules will be developed and finalized before database lock.

The protocol deviations that should be considered as potential IPDs include, but are not limited to:

- Subject was enrolled in the study despite the violation of inclusion/exclusion criteria
- Subject was less than 80% compliant with study drug for non-safety reasons
- Subject received prohibited concomitant medications
- Subject received the wrong treatment or incorrect doses

Occurrence of any of these events should be considered as potential IPDs, but a blinded team should categorize them as IPDs only if they have the potential to significantly affect the completeness, accuracy, or reliability of the study data or that may significantly affect a subject's rights, safety, or well-being.

IPDs (from the site deviation log) will be summarized descriptively based on the FAS and presented by treatment group and overall. Additionally, IPDs will be provided in an individual subject data listing.

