9.3.1.2 Primary Analysis

The primary analysis will be performed using a mixed-effects model for repeated measures (MMRM) with the absolute change from baseline at Day 15, Week 4 and Week 8 as the dependent variable. The model will include treatment group, visit, and treatment-by-visit interaction as fixed effects, with continuous baseline ppFEV₁, continuous baseline SwCl, and comparator group (IVA comparator versus TEZ/IVA comparator) as covariates. The Day 15 Visit will not be included in the estimation of the average treatment effect through Week 8. The model will be estimated using restricted maximum likelihood. Denominator degrees of freedom for the *F*-test for fixed effects will be estimated using the Kenward-Roger approximation². An unstructured covariance structure will be used to model the within-subject errors. If the model estimation does not converge, a compound symmetry covariance structure will be used instead. Conditional on the observed data and covariates, missing data will be assumed to be missing at random; consequently, no imputation of missing data will be performed.

The primary results obtained from the model will be the estimated within-group treatment difference through Week 8 (average of Week 4 and Week 8) for the ELX/TEZ/IVA group. The adjusted means with 2-sided 95% confidence intervals and 2-sided *P* values will be provided. Furthermore, the within-group treatment difference at each post-baseline visit will also be provided, obtained from the model.

The adjusted mean (with SE) obtained from the MMRM analysis at each post-baseline visit up to Week 8 will be plotted by treatment group.

The primary analysis will be conducted with the clinic spirometry data only. An additional analysis may also be performed to include pooled spirometry data obtained in clinic and by Air Next Spirometer, if the Air Next Spirometry data are assessed to be reasonably consistent with clinic spirometry data.

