9.3.1.3 Supportive Analysis

There will be no supportive analysis for the primary efficacy endpoint.

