12 LIST OF APPENDICES

Appendix A: Analysis Visit Windows for Safety and Efficacy Assessment

Table 12-1 Analysis Visit Windows for Safety and Efficacy Assessments

Assessment	Visit ¹	Target Study Day	Analysis Visit Window ^{2,3,4} (in study days)
Safety Assessment			
Serum Chemistry Hematology Standard 12-lead ECG	Day 1 (Baseline)	1	≤1 Pre-dose
	Day 15	15	[1, 22]
	Week 4	29	(22, 43]
	Week 8	57	(43, 71]
	Safety Follow-up	Not applicable	Use nominal visit
Coagulation	Day 1 (Baseline)	1	≤1 Pre-dose
	Week 8	57	[1, 71]
	Safety Follow-up	Not applicable	Use nominal visit
Vital Signs (excluding BMI, Weight, Height)	Day 1 (Baseline)	1	≤1
	Day 15	15	[1,22]
	Week 4	29	(22, 43]
	Week 8	57	(43, 71]
	Safety Follow-up	Not applicable	Use nominal visit
Efficacy Assessment and Pharmacodynamic Assessment			
Spirometry ⁵	Day 1 (Baseline)	1	≤1 Pre-dose
	Day 15	15	(1,22]
	Week 4	29	(22, 43]
	Week 8	57	(43, 71]
	Safety Follow-up	Not applicable	>71
Sweat Chloride	Day 1 (Baseline)	1	≤1 Pre-dose
	Day 15	15	(1,22]
	Week 4	29	(22, 43]
	Week 8	57	(43, 71]
CFQ-R Weight, Height and BMI ⁵	Day 1 (Baseline)	1	≤1
	Day 15	15	(1,22]
	Week 4	29	(22, 43]
	Week 8	57	(43, 71]
	Safety Follow-up	Not applicable	>71
Notes:			
¹ Visit name for analysis purpose is used to report data in tables and figures.			
² The analysis visit windows will be applied using the following rules for both scheduled and unscheduled visits:			
a. If no numerical measurement is available within a visit window, the measurement will be considered missing for the visit.			
b. If there is more than 1 numerical measurement available within a visit window, use the following rules:			
i. The measurement closest to the target day will be used; or			
ii. If there are multiple measurements with the same distance from the target day, the latest measurement will be used. If the latest measurement cannot be determined, then unscheduled visit will be selected.			
³ For measurement collected on the date of first dose of study drug in Treatment Period, if it cannot be determined whether the measurement is before or after the first dose:			
a. Scheduled measurement will be treated as pre-dose observation.			

Table 12-1 Analysis Visit Windows for Safety and Efficacy Assessments

Assessment	Visit ¹	Target Study Day	Analysis Visit Window ^{2,3, 4} (in study days)
b. Unscheduled measurement will be treated as post-dose observation.			

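### Does the within-arm ppFEV1 analysis need a separate check for post-bronchodilator tests that follow a pre-bronchodilator Day 1?

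*Protocol*

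**What the plan says.** Protocol section 11.5.1 intends pre-bronchodilator testing at every visit after screening and covers two lapses. If Day 1 itself was post-bronchodilator, later tests are to be done in that state too. If Day 1 was pre-bronchodilator and the subject forgets at a later visit, "a post-bronchodilator spirometry assessment will be obtained for that visit only, and the visit will not be rescheduled". The state is kept: "Each spirometry assessment will be recorded in the source documents as pre- or post-bronchodilator". Protocol section 9.5 also has bronchodilator use during the study collected and documented.

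The SAP divides spirometry by setting only: "The primary analysis will be conducted with the clinic spirometry data only" (section 9.3.1.2). Section 9.3.1.3 adds: "There will be no supportive analysis for the primary efficacy endpoint". The one sensitivity analysis of this endpoint, in section 9.3.1.4, concerns missing data. When an analysis window holds several tests, Appendix A takes the one nearest the target day, and then: "If there are multiple measurements with the same distance from the target day, the latest measurement will be used". Bronchodilator state plays no part in that choice.

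The primary hypothesis (Protocol 12.1, SAP 7.2) is that the mean change in the triple-combination arm is zero.

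**The concern.** A post-bronchodilator value set against a pre-bronchodilator baseline mixes an acute bronchodilator gain with the change attributed to study drug. The protocol shows that it values matching, because it carries a post-bronchodilator Day 1 forward to later visits. Where matching fails, in the case it expressly accepts, the error runs upward.

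In a between-arm comparison, equal lapses would cancel. The primary test here is against zero within one arm, so randomization gives no such protection. A frequent mismatch would overstate the primary estimate and raise the chance of rejecting a true null, and no planned ppFEV1 analysis would isolate it. The window rule could also keep a mismatched test in preference to a matched one.

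**Working it through.** **Inputs from the documents** (Protocol 12.1, SAP 7.2): 125 subjects in the arm, 10% dropout, SD 7.0, effect 3.0 points, two-sided 0.05. The endpoint averages Week 4 and Week 8.

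**The plan's own figure.** n = 125 × 0.9 = 112.5, taken as 112. SE = 7/√112 = 0.661. The one-sample t-test (noncentral t, 111 df) has power 99.4% at 3.0 points, which agrees with the stated figure of more than 99%. The smallest significant mean change is 1.98 × 0.661 = 1.31 points.

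**Inputs not in the documents.** Let f be the share of Week 4 and Week 8 tests that are post-bronchodilator after a pre-bronchodilator Day 1, and b the acute gain in ppFEV1 points. Both are assumptions: f from 1% to 10%, b from 2 to 8.

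**Upward bias = f × b**, with no offset:

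| f | b | Bias (points) | Share of 3.0 | Bias/SE | Rejection if true change is 0 |
|---|---|---|---|---|---|
| 1% | 2 | 0.02 | 0.7% | 0.03 | 5.0% |
| 2% | 4 | 0.08 | 2.7% | 0.12 | 5.2% |
| 5% | 4 | 0.20 | 6.7% | 0.30 | 6.0% |
| 10% | 4 | 0.40 | 13.3% | 0.60 | 9.2% |
| 10% | 8 | 0.80 | 26.7% | 1.21 | 22.4% |

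The last column follows from the assumed f and b. It is not a property of the plan, and the spread from 5.0% to 22.4% shows that the documents cannot fix it.

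**What the last row requires.** There are 112 × 2 = 224 averaged values, so 10% is about 22 mismatched tests, each gaining 8 points. If 50% to 80% of subjects use bronchodilators (assumed), users would have to forget at 10/80 = 12.5% to 10/50 = 20% of visits.

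**Could mismatch alone produce the primary result?** For the bias to equal 1.31 points, f must be 1.31/b: 44% of tests at b = 3, 26% at b = 5, 16% at b = 8. All lie outside the assumed range.

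**Offset from the opposite mismatch.** If a post-bronchodilator Day 1 is not followed by post-bronchodilator tests, the error runs downward. Let u be the share of users, r the chance of forgetting at any visit (equal and independent across visits), and q the adherence to the Day 1 matching instruction.

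- Upward mismatches: u × r × (1 − r).
- Downward mismatches: u × r × (1 − q) × (1 − r).
- Net bias: q × u × r × (1 − r) × b.

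With u = 0.8, r = 0.05, b = 5 (all assumed), q = 1 gives 0.8 × 0.05 × 0.95 × 5 = 0.19 points, q = 0.5 gives 0.095, and q = 0 gives zero. So f × b is close to an upper bound for given inputs.

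**Window rule.** One spirometry test is scheduled per visit, and a lapsed visit is not repeated. Two tests in one window need an unscheduled test, or an early-termination visit close to a scheduled one, since subjects who stop treatment "will continue to complete all scheduled study visits for assessments following completion of the ETT Visit". The mismatched test must then also be the one selected. This adds little.

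**Control-arm information already planned.** SAP 9.3.1.2 states: "The adjusted mean (with SE) obtained from the MMRM analysis at each post-baseline visit up to Week 8 will be plotted by treatment group". A drift in the control arm would therefore be on view. The between-group ppFEV1 contrast is the second key secondary endpoint (SAP 9.3.2.3). With the same SD and 112 per arm, its SE is 7 × √(2/112) = 0.935 and its power at a 3.0-point difference is 89%.

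**The case for a change.** The strongest case for acting is that the gap is real on the page and cheap to close. Protocol 12.3.3.1 leaves supportive analyses to the SAP, which then plans none. For sweat chloride, SAP 9.3.2.4 does plan a check on doubtful values. The control-arm display is a weak detector: a drift of 0.20 points there would reach significance in about 6% of trials. A count by arm and visit and one further MMRM run would replace an assumption with data, and specifying them before database lock would avoid a post hoc choice of which tests to drop.

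It stands that no planned analysis isolates these tests and that the size of the effect is unknown from the documents. Three things weaken the call for a change.

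- The extra run would not alter the primary analysis, and it is not clearly less biased. If bronchodilator use tracks symptoms, setting those values to missing removes visits selectively.
- The protocol guarantees the per-test state only in source documents. Whether it reaches the database cannot be seen here.
- Naming the lapse among important deviations would capture little. The list in SAP 9.2.7 is open ("The protocol deviations that should be considered as potential IPDs include, but are not limited to"), but an event counts only if it could significantly affect the data or the subject. One mismatched value with a 3- to 5-point gain moves the arm mean by 3/224 = 0.013 to 5/224 = 0.022 points, and the post-bronchodilator test is what the protocol prescribes in that situation.

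**Conclusion.** No change to the plan follows. Protocol 11.5.1 makes a fair trade-off: it keeps the visit and records the state, where rescheduling or discarding the test would cost data. The SAP's silence on bronchodilator state omits one possible check but contradicts nothing. Analysing the data as written still gives a sound conclusion.

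On assumed inputs of 1% to 10% of tests and 2 to 8 points, the upward bias is 0.02 to 0.80 points before any offset from the reverse mismatch. At 1% to 2% of tests it is at most 0.16 points (2% × 8), about a quarter of a standard error. The extreme corner is not trivial, but it needs about 22 of 224 tests mismatched with an 8-point gain each, and it still falls short of the 1.31 points needed for significance. The between-group ppFEV1 test carries no net bias if lapses and gains are alike in the two blinded arms, so a primary result owed to mismatch alone would find no support there.

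This rests on the planning SD of 7.0, on 112 evaluable subjects, and on frequencies and gains that the documents do not supply. If the per-test state turns out to be in the database, the analysts can report a count by arm and visit without amending anything.
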